### 8.1.3.2. Statistical Methodology

The statistical comparisons of the natural log-transformed PK parameters for each analyte between hepatic impaired subjects and healthy controls will be based on the PK Analysis Set for the analyte under evaluation. For each analyte, all subjects with available data for the PK parameter under evaluation will be included in the modeling.

Comparisons of interest are shown in [Table 8-3](#).

**Table 8-3. Statistical Comparisons for Pharmacokinetic Analyses**

Analyte	Parameter	Comparison	
		Test	Reference
Filgotinib	AUC last	Moderately impaired hepatic function	Normal hepatic function
	AUC inf		
	C max		
	AUC last	Severely impaired hepatic function	Normal hepatic function
	AUC inf		
	C max		
	AUC last	Mildly impaired hepatic function	Normal hepatic function
	AUC inf		
	C max		
GS-829845	AUC last	Moderately impaired hepatic function	Normal hepatic function
	AUC inf		
	C max		
	AUC last	Severely impaired hepatic function	Normal hepatic function
	AUC inf		
	C max		
	AUC last	Mildly impaired hepatic function	Normal hepatic function
	AUC inf		
	C max		

For each analyte and each PK parameter, a parametric (normal theory) analysis of variance (ANOVA) model will be fitted to the natural log-transformed values of the PK parameter under evaluation.

The statistical model will include hepatic function group as a fixed effect.

The following SAS® PROC MIXED code will provide the comparison between the hepatic function groups and the 90% CI calculations for natural log-transformed PK parameters.

```
proc mixed;  
  by analyte paramcd;  
  class subjid hepaticgrp;  
  model lnest = hepaticgrp / ddfm = kr;  
  repeated / group = hepaticgrp  
  lsmeans hepaticgrp / e diff cl alpha = 0.1;  
  estimate 'Impaired versus Normal' hepaticgrp 1 -1 / cl alpha = 0.10;  
  ods output Estimates = LS_Diffs LSMeans = LS_Means CovParms = MSE;  
run;
```

The ESTIMATE statement will be used to produce the point estimate and the corresponding 90% CI of the difference in PK parameters of interest on a logarithmic scale. The test-to-reference ratio and associated 90% CI will be calculated by taking the exponential of the point estimate and the corresponding lower and upper limits, which is consistent with the two one-sided tests approach {[U.S. Department of Health and Human Services Food and Drug Administration Center for Drug Evaluation and Research \(CDER\) 2001](#), [U.S. Department of Health and Human Services Food and Drug Administration Center for Drug Evaluation and Research \(CDER\) 2003](#)}.

Nonparametric analyses for the PK parameters CL/F, Vz/F, and  $t_{1/2}$ , are routinely performed. When needed, these analyses can be performed using the Wilcoxon rank sum test for parallel design between the test and reference groups for filgotinib and GS-829845.

```
proc npar1way data=param wilcoxon;  
  class hepaticgrp;  
  var aval;  
run;
```

To evaluate the protein binding of filgotinib and GS-829845, the percent of unbound filgotinib and GS-829845 at  $T_{max}$  and a later time point will be summarized by time point and hepatic function group. Protein binding data for individual subject will be presented in a listing.

For subjects with hepatic impairment, the relationship between plasma PK exposure parameters ( $AUC_{last}$ ,  $AUC_{inf}$  and  $C_{max}$ ) and overall CPT impairment score may be explored using Spearman correlation analysis and examined graphically. The relationship between the PK parameters

( $AUC_{last}$ ,  $AUC_{inf}$  and  $C_{max}$ ) and baseline lab tests (albumin, total bilirubin, prothrombin time, and International Normalized Ratio [INR]) will be also explored using Spearman correlation analysis and examined graphically for hepatic impaired subjects and for all subjects by hepatic function group.

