Plasma PK parameters for filgotinib and GS-829845 will be listed and summarized by hepatic function group (normal or CPT Class A, B, or C) using descriptive statistics (eg, sample size, arithmetic mean, geometric mean, % coefficient of variation [CV], standard deviation [SD], median, minimum, and maximum).

An analysis of variance appropriate for a parallel design will be fit to the natural logarithm-transformed PK parameters (AUC_{last} , AUC_{inf} , and C_{max}) for filgotinib and GS-829845. The 90% confidence intervals (CIs) will be constructed for the geometric least-squares mean (GLSM) ratio of PK parameters for filgotinib and GS-829845 in groups of subjects with hepatic impairment versus matched controls.

Protein binding of filgotinib and GS-829845 at their T_{max} and another later time point will be summarized by hepatic function group using descriptive statistics.

Safety:

Safety data will be listed by subject and summarized by hepatic function group (normal or CPT Class A, B, or C) and frequency of event/abnormality or descriptive statistical summaries, as appropriate.

Sample Size:

With 16 (8 per group) evaluable subjects, the estimated two-sided 90% CI of the geometric least-square mean (GLSM) ratio of test vs reference groups, with regards to PK parameters (AUC and C_{max}) would be within (50%, 200%) with over 95% probability, if the estimated GLSM ratio were 1.0. This is assuming the SDs for PK parameters between subjects within each group is no more than 0.347 (or 0.203) for the natural logarithm-transformed PK parameters for filgotinib (or GS-829845). Such assumptions are supported by PK data from a prior Gilead study of filgotinib (GS-US-417-3900) with 100 mg dose in healthy volunteers.

An overage of 2 subjects per group will be enrolled in order to accommodate subject drop-outs, so a total sample size of 20 subjects (10 per group) for each cohort will be required.

This study will be conducted in accordance with the guidelines of Good Clinical Practices (GCPs) including archiving of essential documents.

GLOSSARY OF ABBREVIATIONS AND DEFINITION OF TERMS

λ_z	terminal elimination rate constant, estimated by linear regression of the terminal elimination phase of the log concentration versus time curve of the drug
%AUC _{exp}	percentage of AUC extrapolated between AUC _{last} and AUC _{inf}
°C	degrees Celsius
°F	degrees Fahrenheit
AE	adverse event
ALT	alanine aminotransferase (previously serum glutamic pyruvic transaminase)

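### If Cohort 2 or 3 enrols, the single two-coefficient ESTIMATE in SAP 8.1.3.2, fitted to all groups at once, can supply at most 6 of the 12 or 18 comparisons in Table 8-3, and the group order that decides which ones is not stated

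*SAP*

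**What the plan says.** Table 8-3 of the SAP sets each impaired group (moderate, severe, mild) against normal hepatic function, for AUClast, AUCinf and Cmax of filgotinib and GS-829845. SAP 1.3 makes Cohorts 2 and 3 optional after review of Cohort 1, so there may be two, three or four hepatic function groups.

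On the data in the model, SAP 8.1.3.2 says that for each analyte "all subjects with available data for the PK parameter under evaluation will be included in the modeling". The PROC MIXED code is split only "by analyte paramcd". Its group statements are "repeated / group = hepaticgrp", "lsmeans hepaticgrp / e diff cl alpha = 0.1" and the single contrast "estimate 'Impaired versus Normal' hepaticgrp 1 -1 / cl alpha = 0.10". The text then names the source of the reported result: "The ESTIMATE statement will be used to produce the point estimate and the corresponding 90% CI". The saved output is "ods output Estimates = LS_Diffs LSMeans = LS_Means CovParms = MSE", which leaves out the table of pairwise differences.

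Neither document gives the values of `hepaticgrp` or their order, and the CLASS statement has no ORDER= option. The wording for the groups varies. Table 8-3 uses mildly, moderately and severely impaired, and normal. The protocol synopsis has results "summarized by hepatic function group (normal or CPT Class A, B, or C"). SAP 1.3 and the opening of SAP 8.1.3.2 speak of healthy controls.

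**The concern.** A contrast with two coefficients on a factor with three or four levels gives the first level minus the second and sets the rest to zero. It cannot deliver two or three impaired-versus-normal comparisons from one fit. Which comparison it does deliver depends on a level order that the plan leaves open.

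These ratios are the primary endpoints, and Protocol 8.7 bases the [50%, 200%] conclusion on their 90% CIs. Coefficients 1, -1, 0, 0 sum to zero, so the contrast is estimable and the program runs without complaint. A difference between two impaired groups would print under a label that says impaired versus normal. The sensitivity analysis in SAP 8.1.4 repeats the same group comparisons and would carry the same gap.

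**Working it through.** **1. The plan's own figure.** SAP 1.4 states a probability over 95% for a two-group comparison with 8 evaluable subjects per group. Inputs: log-scale SD 0.347, bounds ±ln 2 = ±0.693, true ratio 1.0, df = 14. SE = 0.347 × √(2/8) = 0.1735. The exact two one-sided tests calculation gives 96.8% for filgotinib, and above 99.9% for GS-829845 (SD 0.203). The figure is reproduced and is not affected by this point.

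**2. Comparisons needed and rows returned.** Needed: 2 analytes × 3 parameters = 6 per impaired group. That is 6 for Cohort 1 alone, 12 with one adaptive cohort and 18 with both. Returned: one contrast in each of 2 × 3 BY groups = 6 rows. With all groups in one fit, the ceiling is therefore 6 of 12 or 6 of 18 under any level order.

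**3. What the 6 rows contain, over all level orders.** The contrast is right if normal is second, inverted if normal is first, and between two impaired groups otherwise.

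| Groups in the fit | Orders | Impaired minus normal | Inverted | Two impaired groups |
|---|---|---|---|---|
| 2 | 2 | 1 | 1 | 0 |
| 3 | 6 | 2 | 2 | 2 |
| 4 | 24 | 6 | 6 | 12 |

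**4. Examples under default sorting.** The labels below are wording taken from the documents. None is a documented value of `hepaticgrp`. Each cell gives the contrast and the number of Table 8-3 comparisons supplied in the right direction.

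| Cohorts (needed) | Table 8-3 wording | CPT-class wording | Controls labelled 'Healthy…' |
|---|---|---|---|
| 1 (6) | moderate − normal: 6 | moderate − normal: 6 | normal − moderate: 0, 6 inverted |
| 1+2 (12) | moderate − normal: 6 | moderate − severe: 0 | normal − moderate: 0, 6 inverted |
| 1+3 (12) | mild − moderate: 0 | mild − moderate: 0 | normal − mild: 0, 6 inverted |
| 1+2+3 (18) | mild − moderate: 0 | mild − moderate: 0 | normal − mild: 0, 6 inverted |

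**5. Run pair by pair instead.** Under Table 8-3 wording, mild and moderate sort before normal and are right, while severe sorts after it and is inverted. Under CPT-class wording all three pairs are right. With a 'Healthy…' label all three invert. Since 1/0.5 = 2 and 1/2 = 0.5, an interval lies inside [50%, 200%] exactly when its reciprocal does, so inversion leaves that conclusion unchanged.

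**6. Size of a mislabelled row.** This needs true ratios that the documents do not give. If all are 1.0, every row reads about 1.00 and the slip cannot be seen; Protocol 1.3 expects no significant change in exposure. With assumed ratios of 1.1 (mild), 1.4 (moderate) and 1.8 (severe), mild/moderate reads 1.1/1.4 = 0.79, moderate/severe reads 1.4/1.8 = 0.78, and an inverted severe row reads 1/1.8 = 0.56.

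**7. Whether the needed results exist elsewhere in the output.** LSMEANS with DIFF and CL prints every pairwise difference with 90% limits. The intervals can also be rebuilt from the saved LSMeans table. Because each group has its own variance, the group means are independent, so SE(difference) = √(SE₁² + SE₂²) and df = (SE₁² + SE₂²)² / (SE₁⁴/df₁ + SE₂⁴/df₂).

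**The case against.** The strongest reply is that the code is a schematic for one pair, to be run for each row of Table 8-3. Much supports this. The table is laid out as test and reference, the contrast label names two groups, and PROC MIXED names no input data set. SAP 1.4 sizes a two-group comparison. Protocol 8.7 compares an impaired group with its matched controls, and SAP 2.4 says no change from the protocol is planned. The Wilcoxon code that follows is plainly schematic, since it omits even the split by analyte and parameter. The sentence on subjects with available data can also be read as a missing-data rule, not as an instruction to fit all groups together.

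This makes the template reading plausible and narrows the point. It does not remove it, because the SAP nowhere says that the model is run per pair, and the sentence on included subjects and the BY line, taken literally, point to one fit. On either reading the direction still depends on an unstated order.

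The second reply is that LSMEANS already computes what is needed. That stands, as step 7 shows. The remaining gap is that the text names ESTIMATE as the source and the pairwise table is not saved.

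**Conclusion.** The point holds, conditional on Cohort 2 or 3 enrolling. Followed literally, with all groups in one fit, the designated line gives at most 6 of 12 or 6 of 18 comparisons, and its label may not match its content. On the pair-by-pair reading, what remains is a possible reversal of direction that does not alter the [50%, 200%] conclusion. Severity is minor to should-fix, with moderate confidence, because the intended reading is uncertain and the needed intervals can be obtained from the same model.

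A reader might infer more than the documents support:

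- That the code yields none of the 18 comparisons. This needs both the all-groups reading and particular labels.
- That the line never involves normal subjects once the mild cohort is present. In 12 of the 24 four-group orders it does, 6 correctly and 6 inverted.
- That Cohort 1 alone is safe. It is under Table 8-3 or CPT-class wording, but a 'Healthy…' label would invert it.
- That the 90% CIs cannot be recovered. They are printed by LSMEANS and can be rebuilt from saved output.

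Whether the reference should be each cohort's matched controls or all normal controls is a separate trade-off and not part of this finding.

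**What to change.** State the values and order of `hepaticgrp`, including any ORDER= option. Then do one of the following.

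(a) Write one labelled ESTIMATE per impaired group, with +1 on that group, -1 on normal and 0 elsewhere. For the order mild, moderate, normal, severe: mild 1 0 -1 0; moderate 0 1 -1 0; severe 0 0 -1 1. For the order CPT A, B, C, normal: 1 0 0 -1; 0 1 0 -1; 0 0 1 -1. With only moderate, normal, severe: moderate 1 -1 0; severe 0 -1 1. With only mild, moderate, normal: mild 1 0 -1; moderate 0 1 -1.

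(b) State that the two-group code is run separately for each impaired group, with impaired coded first and normal second.

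Given the same controls, (a) and (b) give the same estimate and SE. The difference is the impaired mean minus the normal mean, its variance is s²(impaired)/n + s²(normal)/n with each group's own s² and n, and no other group enters. There is no precision cost.

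Apply the same two-group split to the optional Wilcoxon code, which shows none although the rank sum test compares two groups. The whole change is a few lines of SAP text and code, with no new data.

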#### **8.1.4. Sensitivity Analysis**

Sensitivity analysis will be conducted for the key PK analyses if the PK scientist identifies PK data as questionable.

The natural log-transformed values of plasma PK parameters  $AUC_{last}$ ,  $AUC_{inf}$  and  $C_{max}$  will be used to assess potential outliers. For any specific PK parameter ( $AUC_{last}$ ,  $AUC_{inf}$  or  $C_{max}$ ) of any analyte (filgotinib or GS-829845), the mean of log-transformed parameter values minus 2 times of SD of log-transformed values from all evaluable subjects will be used as the lower bound, while the mean plus 2 times of SD of log-transformed values from all evaluable subjects will be used as the upper bound. Log-transformed values of a specific PK parameter below the lower bound or above the upper bound will be marked as potential data outliers for this PK parameter. Any subject with log-transformed parameter values being marked as potential data outliers for all PK parameters  $AUC_{last}$ ,  $AUC_{inf}$  and  $C_{max}$  for both filgotinib and GS-829845 will be marked as a potential outlying subject.

The sensitivity analysis will include all data excluding ones from the potential outlying subjects. This sensitivity analysis will be denoted as secondary analysis in the TFLs, while the analysis using all data from PK Analysis Sets will be denoted as primary analysis. The sensitivity analysis will consist of the PK parameter summary tables and the tables and listings for statistical comparisons between the hepatic function groups for both filgotinib and GS-829845.

## **10. SOFTWARE**

SAS® Software Version 9.4. SAS Institute Inc., Cary, NC, USA.

Phoenix WinNonlin® 7.0. Pharsight Corporation, Princeton, NJ, USA.

nQuery Advisor(R) Version 6.0. Statistical Solutions, Cork, Ireland.

## 11. SAP REVISION

Revision Date (DD MMM YYYY)	Section	Summary of Revision	Reason for Revision

## 12. APPENDICES

### Appendix 1. Schedule of Assessments

Study Procedure	Screen a	Day -1	Day 1	Days 2-5	Day 6 b	Day 15 (± 1 day) c	ET d
Written Informed Consent	X						
Medical History	X						
Complete Physical Exam	X					X	X
Symptom-Driven Physical Examination e		X	X	X	X		
Height	X						
Weight, BMI	X	X					
Vital Signs f	X	X	X	X g	X	X	X
HIV-1/2, HBV, and HCV Testing	X						
Hematology h	X	X i	X		X	X	X
Chemistry h	X	X i	X		X	X	X
Coagulation h	X	X i	X		X	X	X
α-fetoprotein	X						
Urinalysis	X	X i	X		X	X	X
Serum Pregnancy Test j	X	X i			X	X	X
FSH k	X						
Urine Drug, Cotinine, and Alcohol Screen	X	X i				X	X
12-Lead ECG	X	X	X l		X	X	X
Enrollment m			X				
Study Drug Administration			X				
PK Assessments n			X				X
Review Study Restrictions	X	X			X	X	X
Clinic Confinement			X				
Review AEs & Concomitant Medications o			X				

a Prospective subjects should be screened no more than 28 days prior to administration of the first dose of study drug.

b Subjects will be discharged from the clinic on Day 6, following all morning assessments.

- c Subjects will return for a FU visit on Day 15 ( $\pm$  1 day).
- d Assessments will be performed within 72 hours of early termination (ET) from the study.
- e Symptom-driven PEs will be performed during confinement as needed, based on reported signs and symptoms.
- f Vital signs include blood pressure, heart rate, respiration rate, and body temperature.
- g Day 3 only.
- h Hematology, Chemistry, Coagulation: as specified in study protocol.
- i Two sets of safety labs will be collected upon clinic admission; one will be sent to the central lab and another will be sent to the sites' local lab to obtain results in time for enrollment on Day 1.
- j Females of child-bearing potential only.
- k Female subjects  $\leq$  54 years old with amenorrhea  $>$  12 months.
- l 2 hours postdose.
- m On Day 1, subjects will be enrolled immediately prior to dosing.
- n Intensive PK sampling will occur relative to dosing of filgotinib on Day 1 at the following time points for each cohort: Day 1: 0 (predose,  $\leq$  5 min before dose), 0.5, 1, 2, 3, 4, 5, 6, 8, 12, 18, 24, 36, 48, 72, 96, and 120 hours postdose. A blood sample for PK analysis will be collected at the ET visit (if applicable) and may be analyzed.
- o From the time of obtaining informed consent through the first administration of study drug, record all SAEs, as well as any nonserious AEs related to protocol-mandated procedures on the AE eCRF. All other untoward medical occurrences observed during the screening period, including exacerbation or changes in medical history, are to be captured on the medical history eCRF. See Adverse Events and Toxicity Management in study protocol for additional details.

